9.5. Interim analysis

The first efficacy analysis for study futility will be assessed 3 months after 10 subjects are enrolled.

This study uses a Simon 2-stage minimax design. Interim analysis will be performed 3 months after 10 subjects are enrolled. If 2 or fewer of those 10 patients have a response, the study will be discontinued after Part 1 due to futility.

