This Simon's two-stage design yields a type I error rate of 0.095 and power of 0.802 when the true response rate is 48%. The probability of early stopping due to futility is approximately 49.2%.

Primary Analysis

After a maximally 42 patients are enrolled in the phase 1b and phase 2 portions combined, a primary interim efficacy analysis and the second safety analysis will be conducted. The subset safety analysis will be also descriptively performed based on the previous exposure groups (Dara + Len + Dex or Dara + Pom + Dex).

Overall response rate (ORR) and stringent complete response (sCR)/CR/near CR (nCR) according to IMWG criteria will be determined and corresponding 2-sided 80% exact binomial confidence interval will be calculated. The subset ORR analysis will be also performed based on the previous exposure groups (Dara + Len + Dex or Dara + Pom + Dex).

The Kaplan-Meier (KM) method will be used to estimate the time-to-event endpoints such as time on study (TOS), duration of response (DOR), time to progression (TTP), progression-free survival (PFS) and overall survival (OS) distributions. The subset time-to-endpoint outcome analysis will be also performed using the KM method based on the previous exposure groups (Dara + Len + Dex or Dara + Pom + Dex).

Adverse events and tolerability from all subjects who receive at least one dose of study drug will be evaluated for safety and tolerability. Data will be tabulated to examine the frequency.

Study Sites

1. Hackensack University Medical Center - John Theurer Cancer Center - Hackensack, NJ
2. Georgetown-Lombardi Cancer Center - Washington, DC

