Dexamethasone will be administered at 40 mg once weekly on days 1,8,15 for patients 75 years old and younger and at 20 mg once weekly on days 1,8,15 for patients older than 75. Patients may stay on their currently administered steroid regimen if it does not match the above.

ATRA will be administered in a divided dose of twice daily as an oral formulation at 35.5 mg/m²/day for the phase 1b portion, then escalated to 45mg/m²/day for 3 days. The first administration of ATRA will be given in the morning, two days before the scheduled Dara infusion. The last administration of ATRA will

be given in the evening of the day that Dara was administered (days -2, -1, and 0; day 0 is the day of Dara infusion).

Treatment repeats every 28 days for at least 8 cycles in the absence of disease progression or unacceptable toxicity. Patients achieving stable disease may continue to receive treatment in the absence of disease progression or unacceptable toxicity.

After completion of the study treatment, patients are followed up at 28 days and then every 3 months for up to 12 months. Subjects will be evaluated for disease response during each cycle and at the end of study.

Adverse events (secondary endpoint) will be recorded and graded according to the National Cancer Institute Common Terminology Criteria for Adverse Events (NCI-CTCAE) (Version 5).

Tumor response, based on the investigator's assessment, will be evaluated according to the International Myeloma Working Group (IMWG) response criteria (Durie, 2006) and will be modified (mIMWG) to add criteria for MR (Kyle, 2009) (per Appendix B).

The phase 1b portion will estimate the maximum tolerated dose (MTD) by a standard 3+3 design using data collected in the dose escalation phase. MTD will be defined for each dosing level. A maximum of 2 dose levels are planned (35.5 mg/m²/day to 45 mg/m²/day). For phase 1b the maximum number of evaluable patients is planned to be 12.

The phase 2 portion will evaluate the clinical activity of Dara + Pom + Dex + ATRA. A Simon's two-stage minimax design will be used.

Analysis of biomarkers will also be explored in subjects who consent to participate in the exploratory biomarker study.

All subjects will be maintained on the Pomalidomide pregnancy prevention program (Appendix D) for the duration of the study.

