9.2. Sample Size and Power Considerations

Phase 1b of the study will follow a standard 3 + 3 dose escalation design as described in Section 7.4. With two dose levels, the study will need between 3 and 12 patients depending on toxicities. Patients will be considered evaluable in phase 1b for MTD assessment provided that they have not missed any of their doses of ATRA in Cycle 1, or have had a DLT. Patients who are not considered evaluable as defined above will be replaced.

For the phase 2 portion:

Approximately 20 patients who fulfill the eligibility criteria of the protocol will be enrolled. The phase 2 study will use a Simon 2-stage minimax design, whereby 10 patients will be accrued in the first stage, and ORR assessed, before moving to the next stage. If ≥ 3 objective responses are observed in the first stage, the study will proceed to the next stage; and an additional 10 patients will be accrued. If there are 8 or

more responses among the 20 patients, the combination will be declared worthy for further evaluation. The null hypothesis that the true response rate is 25% or less will be tested against a one-sided alternative of 48% or higher at the one-sided type I error of 0.10. This design yields a type I error rate of 0.096 and power of 0.806 when the true response rate is 48%. The probability of early stopping due to futility is approximately 52.0%.

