¶ Criteria used by Zamagni and colleagues, and expert panel (IMPetUs; Italian Myeloma criteria for PET Use). Baseline positive lesions were identified by presence of focal areas of increased uptake

within bones, with or without any underlying lesion identified by CT and present on at least two consecutive slices. Alternatively, an $\text{SUV}_{\text{max}}=2.5$ within osteolytic CT areas >1 cm in size, or $\text{SUV}_{\text{max}}=1.5$ within osteolytic CT areas ≤ 1 cm in size were considered positive. Imaging should be performed once MRD negativity is determined by MFC or NGS. ||| Derived from international uniform response criteria for multiple myeloma. Minor response definition and clarifications derived from Rajkumar and colleagues. When the only method to measure disease is by serum FLC levels: complete response can be defined as a normal FLC ratio of 0.26 to 1.65 in addition to the complete response criteria listed previously. Very good partial response in such patients requires a $\geq 90\%$ decrease in the difference between involved and uninvolved FLC levels. All response categories require two consecutive assessments made at any time before the institution of any new therapy; all categories also require no known evidence of progressive or new bone lesions or extramedullary plasmacytomas if radiographic studies were performed. Radiographic studies are not required to satisfy these response requirements. Bone marrow assessments do not need to be confirmed. Each category, except for stable disease, will be considered unconfirmed until the confirmatory test is performed. The date of the initial test is considered as the date of response for evaluation of time dependent outcomes such as duration of response.

** All recommendations regarding clinical uses relating to serum FLC levels or FLC ratio are based on results obtained with the validated Freelite test (Binding Site, Birmingham, UK).

†† Presence/absence of clonal cells on immunohistochemistry is based upon the $\kappa/\lambda/L$ ratio. An abnormal κ/λ ratio by immunohistochemistry requires a minimum of 100 plasma cells for analysis. An abnormal ratio reflecting presence of an abnormal clone is κ/λ of $>4:1$ or $<1:2$.

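### The stage 1 futility count is taken on a calendar date with no response window or rule for pending patients, so the stated power of 0.806 is not assured

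*Combined protocol and SAP*

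**What the plan says.** Section 9.2 sets the hypotheses: "The null hypothesis that the true response rate is 25% or less will be tested against a one-sided alternative of 48% or higher". It describes a Simon two-stage design "whereby 10 patients will be accrued in the first stage, and ORR assessed, before moving to the next stage". The continuation rule is: "If ≥ 3 objective responses are observed in the first stage, the study will proceed to the next stage". Success is 8 or more of 20. The operating characteristics follow: "This design yields a type I error rate of 0.096 and power of 0.806 when the true response rate is 48" percent.

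Sections 4.1 and 9.5 give the date of the first count: "Interim analysis will be performed 3 months after 10 subjects are enrolled". With 2 or fewer responders the study is discontinued. The rule is worded as mandatory.

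Three other places determine what can be seen on that date:

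- Appendix B (footnotes to Table 9) requires two consecutive assessments for every response category and adds: "Each category, except for stable disease, will be considered unconfirmed until the confirmatory test is performed".
- Table 1 places the serum and urine myeloma panel on Day 1 of each cycle.
- Section 4.1 sets the length of treatment: "Treatment repeats every 28 days for at least 8 cycles in the absence of disease progression or unacceptable toxicity".

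For the later count, the Protocol Summary (Primary Analysis) says: "After a maximally 42 patients are enrolled in the phase 1b and phase 2 portions combined, a primary interim efficacy analysis" will be done, together with the second safety analysis. Section 9.4 puts that safety analysis 3 months after the next 10 patients are enrolled.

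No section defines a response window for the primary ORR, or says how a patient with an unconfirmed response, or one still on treatment without progression, is treated at either count.

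**The concern.** A Simon design assumes that each patient's outcome is known when it is counted and that one response rate applies at both stages. Here the first count is fixed by the calendar. The tenth patient then has about 91 days of follow-up, hence three post-baseline panels at about Days 29, 57 and 85, against at least 8 planned cycles. A patient who responds later, or whose first response awaits its second assessment, does not yet have a confirmed response.

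The boundary of 3 in 10 would then be applied to a rate below the 48% it was calibrated for. The error runs one way: an active regimen can be stopped for futility on immature data, and a futility stop is hard to reverse. The text also leaves open whether an unconfirmed response counts, so the same ten patients could yield opposite decisions.

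**Working it through.** **Inputs.** From Section 9.2: p0 = 0.25, p1 = 0.48, continue at 3 or more of 10, success at 8 or more of 20. From Sections 4.1 and 9.5: look 3 months after the tenth enrolment. From Table 1: panels every 28 days. Not in the documents, so assumed: the share q of eventual responders confirmed at the look, and the time to response.

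**1. The plan's own figures.** With b(x) the Binomial(10, p) probability of x stage 1 responses:

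Power = Σ over x = 3 to 10 of b(x) · P(Bin(10, p) ≥ 8 − x).

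At p = 0.48 the terms are 0.0782 + 0.1749 + 0.2270 + 0.1850 + 0.0989 + 0.0343 + 0.0070 + 0.0006 = 0.8059 (stated 0.806). At p = 0.25 the sum is 0.0956 (stated 0.096). The early-stop probability at 25% is 0.5256 (stated as about 52.0%). The false-stop probability at 48% is P(Bin(10, 0.48) ≤ 2) = 0.0702.

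**2. Incomplete visibility at the interim only.** If each eventual stage 1 responder is confirmed at the look with probability q, and all are known at the final count:

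Power(q) = Σ b(x) · P(Bin(x, q) ≥ 3) · P(Bin(10, p) ≥ 8 − x); false stop = P(Bin(10, 0.48q) ≤ 2).

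| q | Power at 48% | False stop at 48% | Type I error at 25% | Early stop at 25% |
|---|---|---|---|---|
| 1.00 | 0.806 | 7% | 0.096 | 53% |
| 0.95 | 0.792 | 9% | 0.092 | 56% |
| 0.90 | 0.773 | 12% | 0.088 | 60% |
| 0.80 | 0.719 | 19% | 0.078 | 68% |
| 0.70 | 0.640 | 29% | 0.066 | 75% |

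The power loss stays within 2 points down to q = 0.94 (0.789) and passes 2 points at q = 0.93 (0.785).

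**3. Letting earlier patients have longer follow-up.** With even accrual at rate a per month, patient i has T = 3 + (10 − i)/a months at the look. At a = 1.75 (42 patients in 24 months, Section 4.3) this runs from 3.0 to 8.1 months. At a = 0.83 (20 in 24 months) it runs from 3.0 to 13.8. The rates 0.83 and 1.33 are 20/24 and 32/24, the bounds if only the Dara + Len + Dex group forms the count.

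Assume exponential time to PR with median m among responders. Let N be the number of 28-day panels completed by the look. Then q for patient i is 1 − 2^(−c/m), where c = 28(N − 1) days if confirmation waits for the next cycle panel, and c = 28N if a repeat sample is taken promptly. For the tenth patient with m = 1.5 months (45.7 days), N = 3: q = 1 − 2^(−56/45.7) = 0.57 with next-panel confirmation, and 1 − 2^(−84/45.7) = 0.72 with prompt confirmation.

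Power at 48% for m = 1 / 1.5 / 2 months:

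| Accrual per month | Next-panel confirmation | Prompt repeat |
|---|---|---|
| 1.75 | 0.775 / 0.727 / 0.664 | 0.792 / 0.763 / 0.720 |
| 1.33 | 0.784 / 0.750 / 0.703 | 0.796 / 0.774 / 0.742 |
| 0.83 | 0.791 / 0.772 / 0.746 | 0.799 / 0.786 / 0.767 |

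Every cell is below 0.806. The loss runs from under 1 point to about 14 points.

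**The case against.** **Three months is a real maturation period.** It is the minimum, reached only by the tenth patient; the others have longer. This stands, and it is why the second table is a fairer picture than one common q. The loss shrinks but does not vanish.

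**Confirmation need not wait for the next cycle.** Appendix B allows the two consecutive assessments at any time before new therapy and sets no minimum interval. This also stands. A reader might infer that a PR must be present by Day 57 to be confirmed at the look; the documents do not fix that cut-off, because a response first seen at about Day 85 could be confirmed by a repeat sample before about Day 91. The plan does not schedule such a sample, however.

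**The 0.806 is correct.** It is, for fully observed outcomes. A reader might go further and say that this power is definitely not delivered. The documents give no time to response, so that cannot be shown. Nor does any section state that pending patients are failures; it follows only from a rule that counts patients who have a response and names no other category.

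**The final count.** A reader might infer from the synopsis that the primary analysis is cut on the day the last patient enrols, so that recent patients cannot have confirmed responses. The text does not support this. It gives a sequence, not a data cut; it pairs the analysis with a safety analysis that Section 9.4 places 3 months after enrolment; and its 42 patients span both phases and both prior-exposure groups, so the 20 Simon patients need not be the last enrolled. What remains is that the timing is stated inconsistently and should be aligned.

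**The bias is conservative.** Type I error falls, so no false claim of activity is at risk. The harm is confined to abandoning an active regimen.

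**Conclusion.** The point holds as a gap in a stated decision rule. Sections 4.1 and 9.5 mandate a stop on a calendar-date count, with no response window and no provision for pending or unconfirmed responses. The 0.806 in Section 9.2 is therefore not assured.

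The size is conditional on assumptions the documents do not supply. With an assumed median time to PR of 1 to 2 months, power is about 0.66 to 0.78 at 1.75 enrolments per month with next-panel confirmation, and about 0.74 to 0.80 at 0.83 to 1.33 per month with prompt repeat confirmation. If about 94% or more of eventual stage 1 responders are confirmed at the look, the loss is under 2 points. All these figures belong to the 10/20 design and assume complete data at the final count.

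**What to change.** 1. **Reconcile the design first.** Section 9.2 has 10/20 at 25% versus 48%. The synopsis has 12/28 at 30% versus 50%, and its rule computes to type I error 0.078 at 30% and power 0.665 at 48% (0.730 at 50%), against its stated 0.095 and 0.802. State also which patients form the Simon count.
2. **Define one response window**, of a length chosen and justified by the sponsor, over which the 48% applies. State that only confirmed responses count.
3. **Sections 4.1 and 9.5:** continue at 3 or more confirmed responders. Stop for futility only if confirmed responders plus pending patients total 2 or fewer. Pending means on treatment without PD and either with an unconfirmed response or not yet through the window. In between, hold the decision until enough pending patients resolve.
4. **Protocol Summary (Primary Analysis), Sections 9.3 and 9.4:** make the final Simon count when every patient in it has a confirmed response, PD, discontinuation or a completed window, and align the stated timings.

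If all ten and then all twenty patients are counted over that window, power 0.806 and type I error 0.096 are kept with no change to sample size or boundaries. The boundary must be applied once pending patients resolve: with no effective stage 1 stop, the rule becomes a single stage of 20, with type I error 0.102 (power 0.826).

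The cost is protocol and SAP wording. A close stage 1 decision may come a few months later. No extra patients are needed.

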10. ADVERSE EVENTS

10.1. Monitoring, Recording and Reporting of Adverse Events

Any untoward medical event in a patient administered a pharmaceutical product which does not necessarily have to have a causal relationship with the treatment. An adverse event can be any unfavorable and unintended sign (including abnormal finding or lack of expected pharmacological action), symptom, or disease temporarily associated with the use of a medicinal (investigational or non-investigational) product, whether or not related to that (investigational or non-investigational) product. This includes any occurrence that is new in onset or aggravated in severity from the baseline condition, or abnormal results of any diagnostic procedures, including laboratory test abnormalities. A diagnosis or syndrome should be recorded on the AE page of the eCRF rather than the individual signs or symptoms of the diagnosis or syndrome.

Abuse, withdrawal, sensitivity or toxicity to an investigational product should be reported as an AE. Overdose, accidental or intentional, whether or not it is associated with an AE should be reported on the overdose CRF. Any sequela of an accidental or intentional overdose of an investigational product should be reported as an AE on the AE CRF. If the sequela of an overdose is an SAE, then the overdose and sequela must be reported on an SAE report form and on the AE CRF. In the event of overdose, the subject should be monitored as appropriate and should receive supportive measures as necessary. There is no known specific antidote for Pomalidomide, Daratumumab, or Dexamethasone overdose. Actual treatment should depend on the severity of the clinical situation and the judgement and experience of the treating physician.

All subjects will be monitored for AEs during the study. Assessments may include monitoring of any or all of the following parameters: the subject's clinical symptoms, laboratory, pathological, radiological or surgical findings, physical examination findings, or other appropriate tests and procedures.

All AEs will be recorded by the investigator from the time the subject signs informed consent to at least 30 days after the last dose of POM, DARA, or LD-Dex, and those SAEs made known to the investigator at any time thereafter that are suspected of being related to study IPs (POM, DARA, or LD-Dex). AEs and SAEs will be recorded on the AE page of the CRF and in the subject's source documents. All SAEs, Adverse Events of Special Interest and Special situations including pregnancy, suspected transmission of an infectious agent and those associated with an SAE must be reported to Janssen Drug Safety within 24 hours of the investigator's knowledge of the event by facsimile, or other appropriate method, using the SAE Report Form, or approved equivalent form.

As the sponsor of the Study designee, the Principal Investigator shall be solely responsible for complying, within the required timelines, any safety reporting obligation to competent Health Authorities, IRB/ECs and any participating sub-investigators, as defined in applicable laws and regulations. For the purposes of this section, safety data includes adverse events, product quality complaints (PQCs), and special situations including pregnancies.

The Principal Investigator will provide safety information to Janssen Scientific Affairs, LLC on adverse events, special situations including pregnancies and product quality complaints as defined within this section.

Management of Safety Data

This Study has been designated as an interventional study. As such, all adverse events for Janssen Medicinal Products regardless of causality and special situations excluding those from subjects not exposed to a Janssen Medicinal Product and product quality complaints with or without an adverse event as described in this Exhibit will be reported from the time a subject has signed and dated an Informed Consent Form (ICF) until completion of the subject's last study-related procedure (which may include contact for follow-up safety). Serious adverse events will be reported for 30 days after the last dose of study drug.

For the purposes of this study, the Janssen medicinal product is: DARZALEX Faspro®(daratumumab and hyaluronidase-fihj)

10.2. Evaluation of Adverse Events

An adverse event is any untoward medical occurrence in a clinical study subject administered a medicinal (investigational or non-investigational) product. An adverse event does not necessarily have a causal relationship with the treatment. An adverse event can therefore be any unfavorable and unintended sign (including an abnormal finding), symptom, or disease temporally associated with the use of a medicinal (investigational or non- investigational) product, whether or not related to that medicinal (investigational or non-investigational) product. (Definition per International Conference on Harmonisation [ICH])

This includes any occurrence that is new in onset or aggravated in severity or frequency from the baseline condition, or abnormal results of diagnostic procedures, including laboratory test abnormalities.

10.3. Severity / Intensity

For both AEs and SAEs, the investigator must assess the severity / intensity of the event.

The severity of AEs will be graded based upon the subject's symptoms according to the National Cancer Institute (NCI) Common Terminology Criteria for Adverse Events (CTCAE, Version 5);

https://ctep.cancer.gov/protocoldevelopment/electronic_applications/docs/CTCAE_v5_Quick_Reference_8.5x11.pdf

Adverse events that are not defined in the NCI CTCAE should be evaluated for severity according to the following scale:

- Grade 1 = Mild – transient or mild discomfort; no limitation in activity; no medical intervention/therapy required
- Grade 2 = Moderate – mild to moderate limitation in activity, some assistance may be needed; no or minimal medical intervention/therapy required
- Grade 3 = Severe – marked limitation in activity, some assistance usually required; medical intervention/therapy required, hospitalization is possible
- Grade 4 = Life threatening – extreme limitation in activity, significant assistance required; significant medical intervention/therapy required, hospitalization or hospice care probable
- Grade 5 = Death – the event results in death

The term “severe” is often used to describe the intensity of a specific event (as in mild, moderate, or severe myocardial infarction); the event itself, however, may be of relatively minor medical significance (such as severe headache). This criterion is not the same as “serious” which is based on subject/event outcome or action criteria associated with events that pose a threat to a subject’s life or functioning.

Seriousness, not severity, serves as a guide for defining regulatory obligations.

